#### **10.4. Procedure/Sampling Compliance**

Every attempt will be made to enroll patients who have the ability to understand and comply with instructions. Noncompliant patients may be discontinued from the study.

The collection times of safety assessments, PK and PD samples, and efficacy measurements are given as targets, to be achieved within reasonable limits. The scheduled time points may be subject to minor alterations; however, the actual collection time must be correctly recorded.

The scheduled collection times may be modified by the sponsor based on analysis of the safety and PK information obtained during the study. Any major modifications that might affect the conduct of the study, patient safety, and/or data integrity will be detailed in a protocol amendment.

## 11. Data Management Methods

### 11.1. Data Quality Assurance

To ensure accurate, complete, and reliable data, Lilly or its representatives will do the following:

- provide instructional material to the study sites, as appropriate
- sponsor start-up training to instruct the investigators and study coordinators. This session will give instruction on the protocol, the completion of the CRFs, and study procedures
- make periodic visits to the study site
- be available for consultation and stay in contact with the study site personnel by mail, telephone, and/or fax
- review and evaluate CRF data and/or use standard computer edits to detect errors in data collection.
- conduct a quality review of the database.

In addition, Lilly or its representatives will periodically check a sample of the patient data recorded against source documents at the study site. The study may be audited by Lilly or its representatives and/or regulatory agencies at any time. Investigators will be given notice before an audit occurs.

To ensure the safety of participants in the study, and to ensure accurate, complete, and reliable data, the investigator will keep records of laboratory tests, clinical notes, and patient medical records in the patient files as original source documents for the study. If requested, the investigator will provide the sponsor, applicable regulatory agencies, and applicable IRB/ERBs with direct access to the original source documents.

### 11.2. Data Capture Systems

#### 11.2.1. Case Report Form

An electronic data capture system will be used in this study. The site maintains a separate source for the data entered by the site into the sponsor-provided electronic data capture system.

Any data for which paper documentation provided by the patient will serve as the source document will be identified and documented by each site in that site's study file. Paper documentation provided by the patient may include, for example, a paper diary to collect patient-reported outcome measures (eg, a rating scale), a daily dosing schedule, or an event diary.

For data handled by a data management third-party organization (TPO), CRF data and some or all data that are related will be managed and stored electronically in the TPO system.

Subsequent to the final database lock, validated data will be transferred to the Lilly data warehouse, using standard Lilly file transfer processes.

For data handled by the sponsor internally, CRF data and some or all data that are related will be managed by the sponsor and stored electronically in the sponsor's system.

### ***11.2.2. Ancillary Data***

Data managed by a central vendor will be stored electronically in the central laboratory's database system. Data will subsequently be transferred from the central vendor to the Lilly generic labs system and/or TPO's system.

Bioanalytical data will be stored electronically in the bioanalytical laboratory's database. Data will subsequently be transferred from the bioanalytical laboratory to the Lilly generic labs system and/or TPO's system.

Data from complaint forms submitted to Lilly will be encoded and stored in the global product complaint management system.

## 12. Data Analyses

### 12.1. General Considerations

Statistical analysis of this study will be the responsibility of Lilly.

The interpretation of the study results will be the responsibility of the investigator with the Lilly CRP and/or CRS, pharmacokineticist, and statistician. The CRP and/or CRS and statistician will also be responsible for the appropriate conduct of an internal review for both the final study report and any study-related material to be authorized by Lilly for publication.

The analyses for this study will be descriptive, except for possible exploratory analyses as deemed appropriate. Data analyses will be provided by dose levels and for all patients combined wherever appropriate. For continuous variables, summary statistics will include number of patients (N), mean, median, standard deviation, standard error (SE), minimum, and maximum. Categorical endpoints will be summarized using N, frequency, percentages, and associated SE. Missing data will not be imputed. Exploratory analyses of the data that are not described in the protocol will be conducted as deemed appropriate.

Up to approximately 70 patients may be enrolled in this multicenter Phase 1b/2 study with an open-label, dose escalation design. Patients will be enrolled into cohorts sequentially without randomization to dose level. During dose escalation (Part A), the total samples size per cohort will be determined by DLTs (up to 6 patients per cohort before establishing the MTD). For the tumor-specific expansion cohorts (Part B), additional patients will be enrolled within 3 cohorts for specified tumor types (approximately 15 patients per group). The sample size of approximately 15 patients for the tumor-specific expansion cohorts was selected to allow adequate assessment of safety at the recommended dose and to identify evidence of activity worthy of further investigation in Phase 2.

### 12.2. Patient Disposition

All patient discontinuations will be documented, and the extent of each patient's participation in the study will be reported. If known, a reason for their discontinuation will be given.

### 12.3. Patient Characteristics

Patient characteristics will include a summary of the following:

- Patient demographics including age, sex, screening height and weight, and screening body mass index
- Baseline disease characteristics
- Prior disease-related therapies
- Concomitant medications.

Other patient characteristics will be summarized as deemed appropriate.

## 12.4. Safety Analyses

All patients who receive at least 1 dose of ramucirumab and/or LY2875358 will be evaluated for safety and toxicity. Adverse event terms and severity grades will be assigned by the investigator using NCI CTCAE Version 4.03.

Safety analyses will include summaries of the following:

- AEs, including severity and possible relationship to study drugs
- Dose adjustments
- Laboratory values
- Vital signs
- DLTs at each dose level
- ECG readings.

## 12.5. Pharmacokinetic Analyses

Pharmacokinetic analyses will be conducted on patients who have received at least 1 dose of study drug(s) and have had samples collected.

Population PK models for LY2875358 and ramucirumab may be developed using nonlinear mixed effect modeling. The LY2875358 PK data from this study may be added to data available from other studies, such as the Phase 1 Study JTBA, and the base model for LY2875358 will be the previously developed TMDD model. Noncompartmental methods may also be used if warranted by the data.

The parameters for ramucirumab will include steady-state maximum ( $C_{ss,max}$ ) and steady-state minimum ( $C_{ss,min}$ ) and area under the concentration-time curve during the dosing interval at steady state ( $AUC_{\tau,ss}$ ).

The parameters for LY2875358 may include systemic clearance (CL), volume of distribution (V),  $C_{ss,min}$ , or TMDD model parameters, such as receptor-mediated clearance, non-receptor-mediated clearance, volume of the central compartment, and volume of the peripheral compartment.

Additional exploratory analyses will be performed if warranted by data. These exploratory analyse may include:

- Evaluating the relationship between PK and antitherapeutic antibodies
- Evaluating the relationship between PK and biomarkers, such as MET ECD
- Evaluating the relationship between exposure and response in terms of safety and efficacy (eg, incidence of adverse reactions, PFS, OS, change in tumor size).

The version of any software used for the analysis will be documented, and the program will meet the Lilly requirements of software validation. It is possible that other validated equivalent PK software programs may be used if appropriate, warranted, and approved by Global Pharmacokinetic Management.

## 12.6. Efficacy

The study was not designed to make a comparative efficacy assessment. However, as a co-primary objective for Part B, this study will evaluate preliminary antitumor activity observed with ramucirumab in combination with LY2875358 in the tumor-specific expansion cohorts in terms of ORR. Any tumor response data will be tabulated for Part A and Part B.

## 12.7. Biomarker Analyses

Section 10.2.2 provides a description of the biomarker samples that may be used to carry out biomarker-specific exploratory analyses as mentioned in Section 6.3. Planned exploratory analyses will include, but are not limited to, known or hypothesized biomarkers that are related to VEGF and MET signaling pathways, or tumor biology of the respective tumor types enrolled or associated with sensitivity/resistance to the study drugs.

Across all parts of the study, blood and tissue samples specified (including post-progression-and/or archived tumor samples) may be analyzed to explore potential biomarker(s) associated with response to treatment. Somatic mutation status and/or copy number variations of genes that are targets of the study drug(s), known to be risk factors for cancer, or associated with resistance to anticancer therapies will be analyzed at a laboratory designated by the sponsor. This analysis may employ targeted or whole-exome sequencing approaches.

In Parts B1-4 of the study, tumor-specific biomarker results based on immunohistochemical (IHC), fluorescence in-situ hybridization (FISH), polymerase chain reaction (PCR), or other means for detection and quantitation of cancer-associated protein or nucleic acid changes may be investigated with the aim of identifying genetic variation(s) and/or variations in protein expression that are associated with favorable clinical response within each tumor type or more broadly across multiple tumor types.

All biomarkers will be specifically investigated with the aim of developing a patient stratification strategy that will enable defining a target patient population that is more likely to respond to the treatment regimen being investigated and/or less likely to suffer from TEAEs.

Where applicable, the above associative/correlative assessments involving clinical response and biomarker data may be extended or adjusted to include relevant safety, toxicity, and PK/PD endpoints.

## 12.8. Interim Analyses

An interim analysis will be performed after completion of Part A.

Since this is a dose-finding study, data will be reviewed on a cohort-by-cohort basis during the study until the MTD is determined. The purpose of these cohort-by-cohort reviews is to evaluate the safety data at each dose level and to determine if a DLT has been observed that would suggest MTD has been met or exceeded. Based on these interim results, modifications to the dose escalation strategy or other design elements may be made via protocol amendment to ensure patient safety. The investigators and the Lilly study team will make the determination regarding

dose escalation based upon their review of the safety and tolerability data as described in this protocol.

For Part B, interim analyses will be conducted approximately 3 months after the 15th patient in Parts B1, B2, and B4 (that is gastric, hepatocellular, and non-small cell lung cancers) and approximately 6 months after the 15th patient in Part B3 (renal cell cancer) starts study therapy. Further interim analysis may be considered if deemed appropriate by the sponsor.

## 13. Informed Consent, Ethical Review, and Regulatory Considerations

### 13.1. Informed Consent

The investigator is responsible for ensuring that the patient understands the potential risks and benefits of participating in the study, including answering any questions the patient may have throughout the study and sharing in a timely manner any new information that may be relevant to the patient's willingness to continue his or her participation in the study in a timely manner.

The ICF will be used to explain the potential risks and benefits of study participation to the patient in simple terms before the patient is entered into the study and to document that the patient is satisfied with his or her understanding of the potential risks and benefits of participating in the study and desires to participate in the study.

The investigator is ultimately responsible for ensuring that informed consent is given by each patient before the study is started. This includes obtaining the appropriate signatures and dates on the ICF prior to the performance of any protocol procedures and prior to the administration of study drug.

### 13.2. Ethical Review

Lilly or its representatives must approve all ICFs before they are used at investigative sites. All ICFs must be compliant with the ICH guideline on GCP.

Documentation of ERB approval of the protocol and the ICF must be provided to Lilly before the study may begin at the investigative sites. The ERBs will review the protocol as required.

The study site's ERBs should be provided with the following:

- the current IB, Patient Information Leaflet, or Package Insert, and updates during the course of the study
- ICF
- relevant curricula vitae.

### 13.3. Regulatory Considerations

This study will be conducted in accordance with:

- 1) consensus ethics principles derived from international ethics guidelines, including the Declaration of Helsinki and Council for International Organizations of Medical Sciences International Ethical Guidelines
- 2) the ICH GCP Guideline [E6]
- 3) applicable laws and regulations.

The investigator or designee will promptly submit the protocol to applicable ERBs.

Some of the obligations of the sponsor will be assigned to a TPO.

An identification code assigned by the investigator to each patient will be used in lieu of the patient's name to protect the patient's identity when reporting AEs and/or other study-related data.

### ***13.3.1. Investigator Information***

Site-specific contact information may be provided in a separate document.

### ***13.3.2. Protocol Signatures***

The sponsor's responsible medical officer will approve the protocol, confirming that, to the best of his or her knowledge, the protocol accurately describes the planned design and conduct of the study.

After reading the protocol, each principal investigator will sign the protocol signature page and send a copy of the signed page to a Lilly representative.

### ***13.3.3. Final Report Signature***

The final report coordinating investigator or designee will sign the clinical study report for this study, indicating agreement that, to the best of his or her knowledge, the report accurately describes the conduct and results of the study.

The investigator with the most qualified and evaluable patients will serve as the final report coordinating investigator. If this investigator is unable to fulfill this function, another investigator will be chosen by Lilly to serve as the final report coordinating investigator.

The sponsor's responsible medical officer and statistician will approve the final clinical study report for this study, confirming that, to the best of his or her knowledge, the report accurately describes the conduct and results of the study.

**Attachment 1.     Protocol JTBF Study Schedule**

---

## Screening/Baseline Assessments

Relative Day Prior to Day 1 of Cycle 1	≤28	≤14	≤7	Comments
Informed Consent	X			Informed consent MUST be signed before performing any protocol procedure
Radiological Tumor Assessment (including head-contrasted CT or brain MRI)	X			These scans can be performed locally and may be from prior to consent if taken within 28 days of Day 1, Cycle 1. PET/CT allowed if CT portion is of diagnostic quality
Chest X-Ray	X			May be omitted in patients having a chest CT for their radiological tumor assessment
Functional Tumor Imaging	X			FDG-PET mandatory in Part B1 (gastric). Further functional tumor imaging (including but not limited to DCE-MRI, FLT-PET) is permitted in all patients if appropriate for the respective tumor type at the discretion of the investigator and considered institutional standard of care or is part of an appropriate imaging study open at the site.
Hepatitis B and C Screening	X			Screening is required (see Attachment 2 ); may be from prior to consent if done within 6 months of Day 1, Cycle 1; Hepatitis B surface antigen and hepatitis C (antibodies or RNA according to local standard)
“Post-Progression Tumor Sample” (baseline)	X			Mandatory (see Section 10.2.1 ); may be from prior to consent if taken within 8 weeks of Day 1, Cycle 1. If this is not available, patient must undergo a tumor biopsy pre-study treatment
Archival Tumor Sample	X			Optional (see Section 10.2.2 )
Medical History		X		Including alcohol/tobacco use/other relevant habits
Physical Examination		X		Including height and body weight
Vital Signs		X		Temperature, blood pressure (seated), heart rate, and respiration rate
Performance Status		X		Per ECOG scale (see Attachment 6 )
CTCAE Version 4.03 Grading (Preexisting Conditions)		X		To be reported only after study eligibility is confirmed. Refer to Section 10.1.2 for reporting expectations.
Concomitant Medications		X		See Section 9.5
Local 12-Lead Electrocardiogram		X		Single ECG
Hematology		X		See Attachment 2
Serum Chemistry including calculated creatinine clearance		X		See Attachment 2
Coagulation		X		See Attachment 2
Urinalysis		X		See Attachment 2
Immunogenicity		X		
Sampling for Exploratory Blood Biomarkers		X		See Section 10.2.2
Serum Pregnancy Test			X	Negative serum pregnancy test result required prior to dosing for women of child-bearing potential

Abbreviations: CT = computed tomography; CTCAE = Common Terminology Criteria for Adverse Events; DCE-MRI = dynamic contrasted-enhanced magnetic resonance imaging; ECG = electrocardiogram; ECOG = Eastern Cooperative Oncology Group; FDG-PET = 2-deoxy-2[F-18]fluoro-D-glucose positron emission tomography; FLT-PET = 3-deoxy-3[F-18]fluorothymidine positron emission tomography; PET = positron emission tomography; RNA = ribonucleic acid.

## During- and Post-study Assessments

	Cycle 1					Cycle 2			Cycle 3–n		Short Term Follow-Up Visit 801 a	Comments
Relative Day Within a Cycle	1	2	8 (±1 day)	15 (±1 day)	22	1 (±2 days)	8 (±2 days)	15 (±2 days)	1 (±3 days)	15 (±3 days)		
Ramucirumab	X			X		X		X	X	X		
LY2875358	X			X		X		X	X	X		
Physical Examination	X		X	X		X		X	X		X	All physical examinations should include palpation of the thyroid
Weight	X		X	X		X		X	X	X		
Vital Signs	X	X	X	X		X	X	X	X	X		Temperature, blood pressure (seated), heart rate, and respiration rate
ECOG Performance Status	X					X			X		X	See Attachment 6
Local 12-Lead ECG b	X			X		X		X	X	X		Single ECG at each time point
Hematology c	X		X	X	X	X	X	X	X	X		Predose (see Attachment 2 )
Serum Chemistry c	X		X	X	X	X	X	X	X	X		Predose (see Attachment 2 )
Coagulation c	X		X	X	X	X	X	X	X	X		Predose (see Attachment 2 )
Urinalysis c,d	X		X	X	X	X	X	X	X	X		Predose (see Attachment 2 )
Pregnancy Test						X			X			Serum or urine. Females of childbearing potential only (see Attachment 2 )
Tumor Marker	X					X			X		X	Depending on the respective tumor type (see Attachment 2 )
Hormonal Panel (TSH and fT4)	X					X			X e		X	See Attachment 2
CTCAE Version 4.03 Grading	X					X			X		X	Collected throughout the study as needed. Refer to Section 10.1.2 for reporting expectations
Concomitant Medications	X					X			X		X	Throughout study as needed. See Section 9.5

	Cycle 1					Cycle 2			Cycle 3-n		Short Term Follow-Up Visit 801 a	Comments
Relative Day Within a Cycle	1	2	8 (±1 day)	15 (±1 day)	22	1 (±2 days)	8 (±2 days)	15 (±2 days)	1 (±3 days)	15 (±3 days)		
PK and PD Sampling f	Refer to Attachment 4 and Attachment 7										Refer to Attachment 4 and Attachment 7 for details. No further sampling after Cycle 9 but a sample is required at short term follow up visit (V801)	
Immunogenicity f	X			X		X		X	X		X	See Section 9.2.3.1
Exploratory Blood Biomarker Sampling	X	X	X	X		X		X	X e		X	
Pharmacogenetic Sampling	X											This is a one-time sample which may be taken during Cycles 1 or 2
Optional Tumor Biopsy	X										Throughout study (see Section 10.2.1 )	
Radiological Tumor Assessment g	X										Every 6 weeks after initiation of study treatment; after Cycle 9 every 2-4 cycles as clinically indicated	
Functional Tumor Imaging	X h										FDG-PET mandatory in Part B1 (gastric) 6 weeks after initiation of study therapy	

Abbreviations: CNS = central nervous system; CT = computed tomography; CTCAE = Common Terminology Criteria for Adverse Events; DCE-MRI = dynamic contrasted-enhanced magnetic resonance imaging; ECG = electrocardiogram; ECOG = Eastern Cooperative Oncology Group; FDG-PET = 2-deoxy-2[F-18]fluoro-D-glucose positron emission tomography; FLT-PET = 3-deoxy-3[F-18]fluorothymidine positron emission tomography; fT4 = free thyroxine; PD = pharmacodynamics; PET = positron emission tomography; PK = pharmacokinetics; TSH = thyroid-stimulating hormone; V = visit.

a Short-term follow-up begins on the day after the patient's last dose of study drug and ends approximately 30 days later. This visit should be scheduled  $30 \pm 3$  days after last dose of study drug.

b Electrocardiograms must be recorded before any study drug is administered. In Cycle 1, Day 1 and 15 only, additional ECGs must be recorded pre- and post-LY2875358 infusion, immediately before collecting the corresponding PK samples.

- c Local hematology, coagulation tests, and urinalysis may be done within 2 days prior to administration of study drugs (except Cycle 1, Day 1 [within 3 days]). An additional local chemistry panel according to local standard of care may be done and used for on-study dosing decisions; if done so, chemistry testing must also still be performed by the central laboratory at the regularly scheduled time points. The central chemistry laboratory results will be used for patient eligibility and subsequent safety analyses. In exceptional cases, patient may be enrolled based on local chemistry results after discussion with the sponsor if central laboratory samples results required for eligibility are not available in a timely manner (e.g., due to inclement weather conditions).
- d If, while receiving the investigational product(s), a patient has proteinuria  $\geq 2+$  per a dipstick or routine urinalysis test, a 24-hour urine collection will be conducted prior to the subsequent scheduled treatment (see Section 9.2.3.2.2).
- e Samples will be collected at Cycle 3, Cycle 5, Cycle 7, Cycle 9, and every 4 cycles thereafter while patient is on study treatment.
- f If a patient experiences an infusion-related reaction (see Section 9.2.3.1), immunogenicity samples for anti-ramucirumab and anti-LY2875358 antibodies and PK samples will be taken as close to the onset of the event as possible, at the resolution of the event, and approximately 30 days following the event.
- g The method of assessment used at baseline must be used consistently for tumor assessment and will be repeated approximately every 6 weeks ( $\pm 7$  days) during the study treatment period for lesions outside the CNS. For those patients with known CNS metastases, ongoing CNS surveillance using the same modality is required approximately every 12 weeks ( $\pm 7$  days). Positron emission tomography /CT is allowed if CT portion is of diagnostic quality.
- h For patients in Part B1 (gastric), the mandatory FDG-PET approximately 6 weeks ( $\pm 7$  days) after initiation of study treatment should be performed only if the baseline FDG-PET demonstrated PET avid lesion(s). Further functional tumor imaging (including but not limited to DCE-MRI, FLT-PET) is permitted throughout the study in all patients if appropriate for the respective tumor type at the discretion of the investigator and considered as institutional standard of care or is part of an appropriate imaging study open at the site.

---

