### **9.2.2.2. Dose-Limiting Toxicity Determination**

Dose-limiting toxicity is defined as an AE during Cycle 1 that is possibly, probably, or definitely related to treatment with LY2875358 in combination with a fixed regimen of ramucirumab and fulfills any 1 of the following criterion using the NCI CTCAE Version 4.03:

- $\geq$ Grade 3 non-hematological toxicity. Exceptions will be made for:
  - nausea, vomiting, diarrhea, constipation, or skin rash that persists for  $\leq$ 3 days following appropriate supportive care intervention
  - Grade 3 hypertension in which systolic BP  $\geq$ 160 mmHg and/or diastolic BP  $\geq$ 100 mmHg persist  $<$ 7 days after intensified antihypertensive therapy is initiated
- Grade 4 hematological toxicity of  $\geq$ 7 days duration
- $\geq$ Grade 3 thrombocytopenia with  $\geq$ Grade 2 bleeding
- Any febrile neutropenia

- Any other significant toxicity deemed by the primary investigator and Lilly clinical research personnel to be dose-limiting (eg, any toxicity that is possibly related to the study medication that requires the withdrawal of the patient from the study during Cycle 1).

Infusion-related reactions (including hypersensitivity reactions and anaphylaxis) should not be considered as DLTs unless the investigator or Lilly medical monitor provides compelling rationale to support their inclusion as a DLT.

Patients in Part A (Cycle 2 or greater) and Part B will be evaluated on an ongoing basis for AEs. In these patients, a DLT-equivalent toxicity will be defined based on trends of any clinical significant toxicity deemed by the study investigators and Lilly clinical research personnel to be dose-limiting and related to study drug(s). The investigators and Lilly CRP/CRS will have to agree as to whether such AEs are considered as DLT-equivalent.

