#### **9.2.2.3. Dose Escalation Method and Maximum Tolerated Dose Definition**

In this study, a 3+3 dose-escalation paradigm will be utilized. If 1 patient, at any dose level, experiences a DLT during the DLT period (Cycle 1), then up to 3 additional patients will be enrolled at that dose level. If a DLT is observed in  $\geq 2$  out of 6 patients at any dose level, dose escalation will cease and either the previous dose level will be declared the maximum tolerated dose (MTD) or, following discussions between the investigators and the sponsor, additional patients may be treated at intermediate doses between the previous and the current dose levels.

The first patient enrolled in Part A in this study will be observed for a DLT (as defined in Section 9.2.2.2) during the first 14 days of Cycle 1, before subsequent patients are treated at that dose level. If the first patient does not experience a DLT during this period, subsequent patients may be concurrently enrolled at the initial cohort. In subsequent cohorts, all patients may be enrolled concurrently.

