#### 10.1.1. Safety Data Collection and Review

Investigators are responsible for monitoring the safety of patients who have entered into this study and for alerting Lilly or its designee to any event that seems unusual, even if this event may be considered an unanticipated benefit to the patient.

The investigator is responsible for the appropriate medical care of the patient during the study.

The investigator remains responsible for following, through an appropriate health care option, AEs that are serious, considered related to study treatment or the study, or that caused the patient to discontinue before completing the study. The patient should be followed until the event is resolved, the event is no longer considered to be drug-related, the event becomes stable or returns to baseline, a new treatment is initiated for the patient, or the patient dies or is lost to follow-up. Frequency of AE and SAE follow-up evaluation is left to the discretion of the investigator.

The timing of all safety evaluations is shown in the Study Schedule ([Attachment 1](#)). [Table JTBF.4](#) presents a summary of AE and SAE reporting guidelines. [Table JTBF.4](#) also shows which database or system is used to store AE and SAE data.

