### Pharmacokinetic and Pharmacodynamic Sampling Schedule

Study Period		Approximate Running Time (h) a	Unique Sample ID	Sample Description	LY2875358	Ram	MET ECD
Cycle 1	Day 1	0	1	Pre-Ramucirumab Infusion	X	X	X
		1	2	End of Ramucirumab Infusion	X	X	X
Minimum of approximately 60 minutes between infusions							
		2	3	Pre-LY2875358 Infusion b	X	X	
		3.5	4	End of LY2875358 Infusion (EOI)	X	X	X
		6.5	5	3 h Post-LY2875358 EOI	X	X	
		8.5	6	5 h Post-LY2875358 EOI	X	X	
		11.5	7	8 h Post-LY2875358 EOI	X	X	
	Day 2	24	8	21 h Post-LY2875358 EOI	X	X	X
	Day 8	168	9	Anytime on Day 8	X	X	X
Day 15	0	10	10	Pre-Ramucirumab Infusion	X	X	X
		1	11	End of Ramucirumab Infusion	X	X	X
Minimum of approximately 60 minutes between infusions							
		2	12	Pre-LY2875358 Infusion b	X	X	
		3.5	13	End of LY2875358 Infusion (EOI)	X	X	X
		6.5	14	3 h Post-LY2875358 EOI	X	X	
		8.5	15	5 h Post-LY2875358 EOI	X	X	
	Day 22	168	16	Anytime on Day 22	X	X	X
Cycle 2	Day 1	0	17	Pre-Ramucirumab Infusion	X	X	X
		1	18	End of Ramucirumab Infusion	X	X	X
Minimum of approximately 30 minutes between infusions							
		1.5	19	Pre-LY2875358 Infusion b	X	X	
		3	20	End of LY2875358 Infusion	X	X	X
	Day 8	168	21	Anytime on Day 8	X	X	X
	Day 15	0	22	Pre-Ramucirumab Infusion	X	X	X
		1	23	End of Ramucirumab Infusion	X	X	X
Minimum of approximately 30 minutes between infusions							
		1.5	24	Pre-LY2875358 Infusion b	X	X	
		3	25	End of LY2875358 Infusion	X	X	X

Study Period		Approximate Running Time (h)*	Unique Sample ID	Sample Description	LY2875358	Ram	MET ECD
Cycle 3	Day1	0	26	Pre-Ramucirumab Infusion	X	X	X
		1	27	End of Ramucirumab Infusion	X	X	X
Minimum of approximately 30 minutes between infusions							
		1.5	28	Pre-LY2875358 Infusion b	X	X	
		3	29	End of LY2875358 Infusion (EOI)	X	X	X
	Day 15	0	30	Pre-Ramucirumab Infusion	X	X	X
		1	31	End of Ramucirumab Infusion	X	X	X
Minimum of approximately 30 minutes between infusions							
		1.5	32	Pre-LY2875358 Infusion b	X	X	
		3	33	End of LY2875358 Infusion (EOI)	X	X	X
Cycle 5	Day1	0	34	Pre-Ramucirumab Infusion	X	X	X
		1	35	End of Ramucirumab Infusion	X	X	X
Minimum of approximately 30 minutes between infusions							
		1.5	36	Pre-LY2875358 Infusion b	X	X	
		3	37	End of LY2875358 Infusion (EOI)	X	X	X
	Day 15	0	38	Pre-Ramucirumab Infusion	X	X	X
		1	39	End of Ramucirumab Infusion	X	X	X

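### The Grade 3 hypertension DLT exception turns on 7 days, but no blood pressure is scheduled for the 14 days between Cycle 1 Day 15 and Cycle 2 Day 1

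*Protocol*

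**What the plan says.** Protocol 9.2.2.2 sets the window: "Dose-limiting toxicity is defined as an AE during Cycle 1". Non-hematological toxicity of Grade 3 or higher counts, with listed exceptions. One exception is Grade 3 hypertension in which the raised pressure lasts less than "7 days after intensified antihypertensive therapy is initiated". SAP 6.11 repeats the rule.

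Blood pressure is collected through the Vital Signs row of Attachment 1, During- and Post-study Assessments ("Temperature, blood pressure (seated), heart rate, and respiration rate"). That row is marked on Cycle 1 Days 1, 2, 8 and 15, blank on Day 22, and marked again on Cycle 2 Days 1, 8 and 15.

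The patient does attend on Day 22. Hematology, chemistry, coagulation and urinalysis are marked in the same table, and Attachment 4 lists a PK and MET ECD sample described as "Anytime on Day 22".

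Unscheduled follow-up is permitted. Protocol 10.1.1 states: "Frequency of AE and SAE follow-up evaluation is left to the discretion of the investigator". The CTCAE grading row of Attachment 1 is annotated "Collected throughout the study as needed".

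**The concern.** A rule that depends on whether raised pressure lasted 7 days needs a measurement somewhere near day 7. After the second ramucirumab dose on Day 15, the schedule offers none for two weeks, although the patient is on site halfway through for blood and urine.

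The DLT count drives the 3+3 decisions in Protocol 9.2.2.3. After one DLT, "then up to 3 additional patients will be enrolled at that dose level"; two or more in six stop escalation. Changing one patient's classification therefore turns 0/3 into 1/3, which expands the cohort, or 1/6 into 2/6, which ends escalation. The recommended dose range is the primary objective, and the protocol itself treats hypertension as a known risk of ramucirumab.

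**Working it through.** The plan states no figure to reproduce. The check compares the schedule with the length of time the rule must resolve.

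**Inputs.** Visit days and windows come from Attachment 1: Day 8 ±1, Day 15 ±1, Cycle 2 Day 1 ±2. Day 22 has no printed window. Cycle 1 is 28 days, so Cycle 2 Day 1 is nominally Day 29. The rule's limit is 7 days.

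**Intervals between scheduled blood pressures.** Nominal interval = later day − earlier day. The extremes use the window limits.

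| From | To | Nominal (days) | With windows (days) |
|---|---|---|---|
| Day 1 | Day 2 | 2 − 1 = 1 | 1 |
| Day 2 | Day 8 | 8 − 2 = 6 | 7 − 2 = 5 to 9 − 2 = 7 |
| Day 8 | Day 15 | 15 − 8 = 7 | 14 − 9 = 5 to 16 − 7 = 9 |
| Day 15 | Cycle 2 Day 1 | 29 − 15 = 14 | 27 − 16 = 11 to 31 − 14 = 17 |

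Hypertension found by Day 8 has a scheduled reading about a week later. Hypertension found on Day 15 does not.

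**Is the blank cell consistent with its neighbours?** Hematology is marked on Cycle 1 Days 1, 8, 15 and 22, Cycle 2 Days 1, 8 and 15, and Days 1 and 15 of later cycles. Vital Signs are marked at every one of those visits except Day 22. The other laboratory-only visits (Day 8 of Cycles 1 and 2) have both.

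**What the scheduled data can show when therapy is intensified on Day 15:**

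- Pressure still raised at Cycle 2 Day 1: it was raised at least 11 days after intensification. Assuming no remission in between, that exceeds 7 days and points to a DLT.
- Pressure normal at Cycle 2 Day 1, with an unscheduled reading in between: classification may be possible, depending on when that reading was taken.
- Pressure normal at Cycle 2 Day 1, with no unscheduled reading: the duration lies anywhere from 0 to 14 days (nominal). That range spans the limit, so the condition is undetermined.

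**Does another section require a reading in the gap?** The hypertension guidance in Protocol 9.2.3.2.1 has time limits of more than 3 weeks (Grade 3 without symptoms) and more than 4 weeks (poorly controlled). Neither calls for a reading at about one week. Attachment 1 has footnotes prescribing triggered follow-up for proteinuria and infusion-related reactions, but none for hypertension.

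**With a reading on Day 22.** Day 15 to Day 22 is 22 − 15 = 7 days (22 − 16 = 6 to 22 − 14 = 8). Day 22 to Cycle 2 Day 1 is 29 − 22 = 7 days (27 − 22 = 5 to 31 − 22 = 9). At nominal timing, a raised Day 22 reading shows the limit was reached, and a normal one bounds the duration at 7 days instead of 14. This matches the spacing already used from Day 8 to Day 15.

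**The case against.** The strongest reply is that the protocol does not rely on scheduled visits to time adverse events. Follow-up is allowed at any frequency the investigator chooses, and the 7-day clock starts only when an investigator has just intensified therapy, so that patient is under active care. The same list of exceptions contains a 3-day limit for gastrointestinal symptoms and rash, which weekly visits could not resolve either. This stands as far as it goes. A reader might infer that the next reading of any kind is 14 days away, or that such events cannot be classified. The documents support neither: only the next scheduled reading is 14 days away, and an event still present at Cycle 2 Day 1 points to a DLT. But permission is not a requirement. A patient can report when nausea or a rash ended, whereas asymptomatic raised pressure has to be measured.

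Second, because under 7 days is an exception, an undocumented exception could be read as not applying, so that the event counts as a DLT. That is a plausible reading, but the text does not state it, and it would count an event that resolved within days.

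Third, a Day 22 reading falls 6 to 8 days after a Day 15 intensification. A raised value at 6 days or a normal one at 8 still leaves the question open. This is correct. It is also why the next weekly visit should not be made the deciding reading: with therapy intensified on Day 12, Day 15 is only 3 days later.

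Fourth, Part A may be over. SAP 5.1 (approved November 2014) describes the NSCLC cohort as added in light of Part A safety and tolerability, and the current protocol dates from March 2015. A schedule change now may therefore affect no escalation decision. The documents do not say that Part A enrolment has closed.

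**Conclusion.** The mismatch is real but narrow. The schedule does not guarantee the reading that the exception needs. The open case is hypertension found on or after Cycle 1 Day 15, resolved by Cycle 2 Day 1, with no unscheduled reading in between. Separately, asymptomatic hypertension arising after Day 15 may not be seen until Cycle 2 Day 1.

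The size is a 14-day scheduled gap (11 to 17) against a 7-day rule. How often the open case would occur cannot be estimated from the documents. A reader might take the hypertension rates in Protocol 5.2.1 as Cycle 1 Grade 3 rates, but they are not. The 16% in the gastric study is not restricted to Grade 3 (8% on placebo). The 14% (treatment-related Grade 3 or higher, HCC) and 7.7% (Grade 3, RCC) are study-level results, not limited to Cycle 1.

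The conclusion assumes that no source outside these documents sets a monitoring interval. Protocol 9.2.3.2.9 refers investigators to blood pressure guidance in the ramucirumab Investigator's Brochure, which was not available. This is an inexpensive improvement to DLT ascertainment and safety detection, not a flaw that invalidates the escalation.

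**What to change.** Reconcile the DLT definition (Protocol 9.2.2.2, SAP 6.11) with Attachment 1:

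- Mark Vital Signs at the existing Cycle 1 Day 22 visit.
- When the hypertension exception is applied, record the date therapy was intensified and the dates of the blood pressure readings relied on.
- Keep the exception as written. Do not add a rule that the next weekly visit decides the classification.
- If Part A enrolment is complete, state in the study report how any hypertension found on or after Cycle 1 Day 15 was classified, and on which readings.

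The cost is one seated set of vital signs per patient at a visit already attended, plus the recorded dates. No threshold or treatment rule changes. The reading reduces the scheduled gap from 14 days to about 7 but does not remove all uncertainty at the 7-day limit.
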